In 2006, Fuchs reported similar results, with improvement in pain and function for both types of infiltration in a randomized study of 56 patients. Pain improvement was faster with corticosteroids (significant at 2 weeks) but slightly better with HA at 26 weeks, with a clearer functional gain for HA mainly at 6 months.

In 2008, in a 3-arm study, one of which was placebo, Heyworth made the same findings but with no significant difference with placebo. He noted an improvement in pain and function in

all 3 groups (18 to 22 patients in each), with a clearer improvement in pain for the HA group at 6 months and in function at 3 and 6 months.

Moreover, the latest study in 2015 by Montfort, concludes that "HA was more effective over time and improved functional status more markedly in patients with severe symptoms".

Concerning the number of HA infiltrations to be administered in rhizarthrosis, a French team led by Roux C showed that there was no difference between groups receiving one, two or three infiltrations at one-week intervals, in terms of neither pain nor function.

Therefore, the 2 types of infiltration appear to be effective, but with different response profiles: corticoids have a rapid analgesic and anti-inflammatory action, whereas HA has a more delayed and sustained action over time. Consequently, it seems appealing to combine these 2 treatments to obtain a synergistic effect. One study demonstrated the benefits of this combination in gonarthrosis, which was more effective on pain than hyaluronic acid alone and there was no difference in functional improvement between the two groups.

Some authors have questioned the potential clinical or histological risks of combining these two drugs, given the risk of reduced chondrocyte proliferation and increased apoptosis which could lead to chondral degradation. However, no increased risks have been reported with this combination, neither clinically nor histologically.

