At the 3-month follow-up visit, the patient will be asked to answer the following question: "Today, compared to the start of treatment (M0), I consider that my thumb:"

- o has worsened
- o has stabilized or had zero improvement
- has improved slightly
- has improved moderately
- has improved significantly
- is healing
- The number of corticosteroid infiltrations over the 12 months of follow-up.

- Recording of adverse effects and events over the 12 months of follow-up.
- Recording of analgesic and NSAID use (number of days taken and cumulative dosage over the week preceding each follow-up visit).
- The number of days off work from the start of orthosis use over the 12 months of follow-up.
- Possible progression to a surgical procedure over the 12 months of follow-up.

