## 4.2.2.3. Patient follow-up

The patient will have a follow-up appointment in 1 month and 6 months post-infiltration with a clinical research nurse or a clinical research technician who will collect pain VAS, Cochin scale, grip and opposition strength, adverse events, and new infiltration data (with the time interval since the initial infiltration). Specific questions will be asked concerning the occurrence of the following adverse events: arthralgia, joint stiffness, joint swelling, and back pain.

The patient will have a follow-up appointment in 3 months and 12 months post-infiltration with the evaluating physician who will perform a clinical examination and collect the pain VAS, Cochin scale, grip and opposition strength, adverse events, and new infiltration data (with the time interval since the initial infiltration). Specific questions will be asked concerning the occurrence of the following adverse events: arthralgia, joint stiffness, joint swelling, and back pain. An ultrasound scan will also be performed at 3 months post-infiltration by the evaluating physician.

The patient's use of treatments (analgesics, NSAIDs) will be recorded in a patient diary for the first 3 months. The use of treatments (analgesics, NSAIDs) will then be recorded in the week preceding the M6 and M12 visits.

If the patient's condition so requires, a further CTC infiltration may be administered at the discretion of the investigator in charge of the patient.

This information will be recorded in the observation book.

If the new infiltration takes place within 3 months of randomization (infiltration according to randomization arm), the patient will be considered a treatment failure (primary endpoint assessed at 3 months).

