# Secondary endpoints:

- Changes in pain at rest and during activity over time will be compared between groups, using random-effects models to account for inter-individual variability modeled via random effects (based on the idea that patients represent a random sample from a larger population), as well as intra-individual variability modeled via measurement error; the group effect (HA + CTC vs. CTC alone), time (M0, M1, M3, M6, M12) and their possible interaction will be estimated and tested.
- Changes in **Cochin scale** parameters, **grip strength** and **opposition strength over** time will be compared between groups using random-effects models. The effect of group (HA + CTC vs. CTC alone), time (M0, M1, M3, M6, M12) and their possible interaction will be estimated and tested.
- The proportion of patients with a change in **ultrasound score** between D0 and M3 will be compared between groups using a Chi2 test.
- The VAS of pain at the time of injection will be compared between the two groups using a Student's t test.
- The number of **new infiltrations** during the follow-up year will be compared between groups using a Student's t test.
- Adverse events will be described for each group in terms of numbers and percentages.
- Changes in **analgesic use** will be compared between groups using random-effects models. The group effect (HA + CTC vs. CTC alone), time (M0, M1, M3, M6, M12) and their possible interaction will be estimated and tested.
- The number of days **off work** during the follow-up year will be compared between groups using a Student's t test.
- The rate of patients undergoing **surgery** will be compared between groups using a Chi2 test.

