#### 9.5. Missing, unused or invalid data accountability process

The number of missing data and the reason for the missing data will be described for each treatment group.

For patients who do not have an available endpoint at inclusion or at M3, the mean VAS of the randomization group will be imputed in order to analyze the entire randomized population in the intention-to-treat analysis.

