### 9.7. Choosing the people to include in analyses

The analysis will focus on the Intention-to-treat population.

A sensitivity analysis on the "Per protocol" population will be performed: exclusion of patients with major protocol deviations (non-administration of all products in the randomization arm, new infiltration less than 3 months after the initial infiltration, possible progression to a surgical procedure less than 3 months after the initial infiltration).

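### New infiltrations are compared by a t test on the yearly count, with no allowance or rule for incomplete follow-up, and the recorded time to re-infiltration is used only at the 3-month cut-off

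*Combined protocol and SAP*

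**What the plan says.** Section 4.1.2 defines the endpoint as a count: "The number of corticosteroid infiltrations over the 12 months of follow-up". Section 9.1, under secondary endpoints, gives its analysis: "The number of new infiltrations during the follow-up year will be compared between groups using a Student's t test". No exposure term, censoring or minimum follow-up is mentioned.

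Section 9.7 sets the population: "The analysis will focus on the Intention-to-treat population". The only missing-data rule is in section 9.5: "For patients who do not have an available endpoint at inclusion or at M3, the mean VAS of the randomization group will be imputed". It concerns the VAS. Nothing is said about counts or about patients who leave before month 12, although section 4.6.1 foresees withdrawal and loss to follow-up and section 5.4.2 allows no replacement.

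Section 4.2.2.3 has the sites collect, at each follow-up visit, "new infiltration data (with the time interval since the initial infiltration"). That timing has two uses. In section 4.2.2.3: "If the new infiltration takes place within 3 months of randomization (infiltration according to randomization arm), the patient will be considered a treatment failure". In section 9.7, among the per-protocol exclusions: "new infiltration less than 3 months after the initial infiltration". No analysis uses it over the rest of the year.

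**The concern.** A count of events depends on how long the patient was observed. A t test on the yearly number gives every patient equal weight as a full year. The plan leaves two readings open for a patient lost early. Keeping the recorded count fits intention to treat, but sets the unobserved months to zero events. Dropping the patient departs from intention to treat, discards observed events, and is safe only if loss is unrelated to outcome. Without a rule, the choice can be made after the data are seen.

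Under the first reading, loss that differs between arms shifts the comparison even when the true rates are equal, and can hide or exaggerate a real difference.

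The second matter is unused information. Section 2.2 motivates the combination by contrasting fast-acting corticosteroids with hyaluronic acid, "whereas HA has a more delayed and sustained action over time". A delay in re-treatment would be relevant to that idea. A yearly total registers a delay only to the extent that it moves events past month 12 or prevents them.

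**Working it through.** **The plan's own figures.** The documents give no rate, SD, power or dropout for new infiltrations, so there is nothing to reproduce for this endpoint. The 132 patients in section 9.2 belong to the primary VAS. They do reproduce: difference 6.4 × (0.35 − 0.25) = 0.64, SD 1.3, two-sided 5%, 80% power gives 65.74 per arm with the t distribution, so 66 per arm and 132 in all. With the 18 extra patients the total is 150, or 75 per arm at 1:1 allocation.

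**Assumptions.** A constant re-infiltration rate λ per year; a fraction d of an arm lost at month 3 (0.25 year), unrelated to outcome; everyone else followed for 12 months; recorded counts kept. One of the loss figures, 12% per arm, is 18/150; the others are illustrative.

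**Expected recorded count.**

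λ × [(1 − d) + 0.25d] = λ × (1 − 0.75d)

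With equal true rates, the ratio of mean counts (combination to control) should be 1:

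- 12% v 12% lost: 0.91/0.91 = 1.00
- control 5%, combination 15%: 0.8875/0.9625 = 0.92
- control 5%, combination 20%: 0.85/0.9625 = 0.88

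With true rates of 0.5 (control) and 0.25 (combination), the true ratio is 0.50:

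- control 20%, combination 5%: (0.25 × 0.9625)/(0.5 × 0.85) = 0.2406/0.4250 = 0.57
- control 5%, combination 20%: (0.25 × 0.85)/(0.5 × 0.9625) = 0.2125/0.4813 = 0.44

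**Simulated rejection rates.** 75 per arm, two-sided 5%, at least 3,000 trials per row. The rate test is z = (a − Nπ)/√[Nπ(1 − π)], where a is the number of events in the combination arm, N the total number of events, and π that arm's share of total follow-up time.

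| Rates per year, control / combination | Lost at month 3, control / combination | t test, recorded counts | t test, completers | Rate test with exposure | Log-rank, first event |
|---|---|---|---|---|---|
| 0.3 / 0.3 | 12% / 12% | 5.2% | 5.3% | 5.3% | 5.3% |
| 0.3 / 0.3 | 5% / 20% | 6.5% | 4.7% | 4.7% | 4.8% |
| 0.5 / 0.5 | 5% / 20% | about 8% | about 5% | about 5% | about 5% |
| 0.3 / 0.3 | 0% / 40% (extreme) | 18.9% | 4.7% | 4.6% | 4.5% |
| 0.5 / 0.25 | 12% / 12% | 65.6% | 64.7% | 67.3% | 59.3% |
| 0.5 / 0.25 | 20% / 5% | 49.5% | 66.4% | 68.3% | 61.5% |
| 0.5 / 0.25 | 5% / 20% | 80.8% | 64.1% | 66.8% | 59.1% |

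Repeat runs place the lowest t-test power at 47% to 50%. The 81% in the last row is no advantage: it comes from the recorded ratio of 0.44, which overstates the true effect of 0.50.

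**Timing.** If half of each arm is re-infiltrated, at mean month 5 v month 9, the t test has about 10% power and the log-rank test about 33%. This rests on event times clustered at assumed months. Under constant rates with equal loss, the table shows the order reversed: 66% for the t test, 59% for the log-rank test.

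**The case against.** A reader might infer that the plan counts a patient lost at month 3 as event-free for the year. The documents do not say so. They are silent, exclusion as missing is equally open, and under the recorded-count reading an infiltration before the loss still counts; only the nine unobserved months become zero.

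A reader might also infer that the interval to re-infiltration is ignored altogether. It is not: it defines treatment failure and a per-protocol exclusion at 3 months. What is missing is any analysis of it beyond that point.

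The inflated type I error needs both the recorded-count reading and unequal loss. Patients and evaluators are blinded, and the documents give no reason to expect unequal loss. With milder imbalance (5% v 10%, or 8% v 15%) at 0.5 per year, the error is only about 5.5 to 6.2%. A t test with 75 per arm is a recognised comparison of mean counts. All of this stands and limits the size of the point. The completer analysis holds 5% here, however, only because the simulated loss is unrelated to outcome.

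Finally, it is tempting to say that a log-rank test should replace the t test. That would change the endpoint of section 4.1.2 from a number to a time, and under constant rates it would cost power. Longer-lasting benefit is also already examined through the models of pain and function to month 12. The documents support adding a time-to-event analysis, not substituting it.

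**Conclusion.** The point holds as a gap in a secondary analysis. The planned test takes no account of follow-up time, no rule covers patients lost before month 12, and the recorded timing goes unanalysed after month 3.

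The bias between arms is nil when loss is equal. With 5% v 20% loss and equal true rates, it amounts to a ratio of mean counts of 0.88 and a type I error of about 7 to 8%. When a true difference exists, the t test's power depends heavily on which arm loses more patients, whereas an exposure-adjusted test is hardly affected. These sizes rest on assumed rates and losses, on loss at month 3 and on recorded counts being kept. The primary VAS comparison at 3 months is untouched.

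**What to change.** In section 9.1, keep the count endpoint of section 4.1.2 but replace the t test by Poisson regression with robust variance, or negative binomial regression, with log follow-up time as offset and adjustment for centre. Include all randomised patients, each contributing events and time up to last contact or 12 months. This supplies the missing rule and stays within intention to treat. Report the rate ratio with its 95% CI, and the number lost before month 12 by arm.

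Add, as supportive, the time from the initial to the first new infiltration, censored at last contact or 12 months: Kaplan-Meier curves, a log-rank test stratified by centre (as the randomisation is), and a Cox hazard ratio with 95% CI.

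The intervals are already collected, so the cost is a few lines in the statistical section and slightly more analysis work.

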# 9.2. Expected number of participants to be included in the research and expected number of participants in each research location with statistical justification.

The study is a superiority trial that focuses on pain reduction at 3 months. This is assessed on the basis of the difference between the two groups in scores measured between 3 months and baseline. Based on data in the literature, we estimate a mean score of  $6.4 \pm 1.3$  at baseline (Montfort, 2014).

According to the same reference, we assume a 25% reduction in pain in the "corticosteroid alone" group, and a 35% reduction in the "corticosteroid and hyaluronic acid combination" group.

To demonstrate this difference with 80% power and 5% alpha risk, 132 patients will be required.

To ensure sufficient power, 18 additional patients will be included in the study, for a total of 150 patients.

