# 2.2. Summary of the results of available non-clinical trials and clinical trials relevant to the biomedical research in question

Rhizarthrosis, or arthrosis of the trapeziometacarpal joint, is a common form of osteoarthritis that affects 10-25% of women, particularly after menopause. It affects unstable joints that are subject to high pressure. It is often bilateral, with frequent asymmetry of clinical and radiological involvement. Pain is located at the anatomical snuffbox, with fluctuating progression and no correlation between radiological and clinical severity. It progresses over several years and can lead to a Z-shaped deformity of the thumb column, which is functionally disabling.

Treatment combines non-pharmacological measures, such as relative resting of the joint, rest orthoses, icing, etc., with pharmacological measures such as analgesics, oral or local non-steroidal anti-inflammatories, or even cortisone or hyaluronic acid infiltrations. The European League Against Rheumatism's (EULAR) recommendations for digital osteoarthritis state that "intra-articular delayed corticosteroid infiltration is effective in painful flare-ups of digital osteoarthritis, particularly of the trapeziometacarpal joint". Both products have been granted marketing authorization, but only corticoids are eligible for reimbursement.

However, no methodologically rigorous studies have tested these infiltrations versus placebo. Only Meenagh has conducted this type of study, but on a small number of patients (2 groups of 20 patients) with small volumes injected (0.25 ml); with no difference noted between the placebo and corticosteroid groups. 

On the other hand, these two types of infiltration have been compared, with both showing efficacy on pain and function.

In 2005, Stahl conducted a randomized study to compare the efficacy of corticosteroid infiltration (CTC) versus hyaluronic acid (HA) and found a reduction in pain in both groups at one month, which was maintained at 6 months. On the other hand, hyaluronic acid infiltration improved functional capacity as early as 3 months and the improvement lasted longer than with corticosteroids.

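### Does powering the trial on a 10-percentage-point pain gap at 3 months, when the dated hyaluronic acid pain advantages are at about 6 months, call for a different primary time point?

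*Combined protocol and SAP*

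**What the plan says.** Section 3.1 sets the main objective at 3 months, and section 9.1 compares activity VAS at M3 in a mixed model with baseline VAS as a fixed effect and center as a random effect. In section 9.2 the baseline is 6.4 with SD 1.3. The effect is introduced with "According to the same reference, we assume a 25% reduction in pain in the" corticosteroid-alone arm, and 35% is assumed for the combination. The reference list shows that source as a comparison of HA with corticosteroid. Section 9.2 then concludes "To demonstrate this difference with 80% power and 5% alpha risk, 132 patients will be required", and 18 more bring the total to 150.

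Section 2.2 summarises earlier trials in this joint:

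- One HA-versus-corticosteroid trial "found a reduction in pain in both groups at one month, which was maintained at 6 months". Its earlier HA gain was in function.
- A second, with 56 patients: "Pain improvement was faster with corticosteroids (significant at 2 weeks) but slightly better with HA at 26 weeks".
- A three-arm trial with placebo "made the same findings but with no significant difference with placebo", "with a clearer improvement in pain for the HA group at 6 months and in function at 3 and 6 months".

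The section infers that corticosteroids act fast, "whereas HA has a more delayed and sustained action over time", and proposes synergy as the reason to combine them. The one study cited as showing a benefit of the combination, in the knee, found a combination "which was more effective on pain than hyaluronic acid alone". Section 2.2 also says that the combination has not been tested in this joint.

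Activity pain at M6 is a secondary objective (section 3.2). It enters a random-effects model over M0, M1, M3, M6 and M12 in which group, time and their interaction are estimated and tested (section 9.1). Section 9.3 gives one 5% level.

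**The concern.** On a first reading, sections 2.2 and 9.2 pull apart. HA is described as late-acting, and both dated pain advantages fall at about 6 months, yet the only confirmatory test is at M3. The 35% has no month and no derivation, and its source cannot have measured a combination arm if the combination is untested in this joint. No M6 contrast, testing order or share of alpha is named.

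If the true gap were small at M3 and larger at M6, the trial would probably miss at M3, could be read as showing no benefit from adding HA, and could not claim the later difference. Because M6 is measured anyway, a second primary time point looks free.

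**Working it through.** **1. The plan's own figure.** Inputs from section 9.2: baseline 6.4, reductions of 25% and 35%, SD 1.3, power 80%, alpha 5%. Allocation is 1:1 (section 4.3.1). The test is taken as two-sided, which section 9.2 does not state; a one-sided test gives 104 and does not fit.

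- Gap = 0.35 × 6.4 − 0.25 × 6.4 = 2.24 − 1.60 = 0.64 points. One percentage point is 0.064.
- Normal approximation: n per arm = 2 × (1.960 + 0.842)² × 1.3² / 0.64² = 64.8, so 65 per arm and 130 in total.
- t test: 65.74, so 66 per arm and 132 in total, as stated.
- Power at 132 is 80.2%. If all 150 are analysed it is 85.0%.

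**2. A smaller M3 gap.** Noncentral t, df = n − 3, with 1.3 assumed as the residual SD given baseline. The standard error at 132 is 1.3 × √(4/132) = 0.226. A gap of 5 percentage points is 0.32, so the noncentrality is 0.32/0.226 = 1.41.

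| True M3 gap (percentage points) | Power, 132 | Power, 150 |
|---|---|---|
| 5 | 29% | 32% |
| 8 | 61% | 67% |
| 10 | 80% | 85% |
| 12 | 92% | 95% |

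Power is sensitive to the gap, as in any trial. The question is whether the documents show that the M3 gap is below 10.

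**3. What the earlier trials can date.** In a trial of HA against corticosteroid, the difference at each visit is the HA effect minus the corticosteroid effect. A late HA lead can arise because the corticosteroid acts early. Here both arms receive corticosteroid and the contrast is HA against saline, so those curves do not fix when an add-on gap appears. The one HA-placebo comparison showed no significant difference with 18 to 22 patients per group, which is inconclusive. An M6 add-on gap of 10 percentage points is therefore no better documented than one at M3.

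**4. Two primary time points.** Suppose M3 and M6 are both primary and tested by Hochberg at 5%: claim both if both p ≤ 0.05, otherwise claim one if its p ≤ 0.025. Assumptions not in the documents: residual SD 1.3 at both visits unless noted, residual correlation 0.5 between visits, complete M6 data. Simulated chance of at least one claim, 132 analysed:

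| Gap at M3 / M6 (percentage points) | M3 only | Hochberg |
|---|---|---|
| 5 / 10 | 29% | 73% |
| 8 / 10 | 61% | 80% |
| 10 / 10 | 80% | 86% |
| 10 / 5 | 80% | 73% |
| 10 / 0 | 80% | 72% |
| 8 / 6 | 61% | 59% |
| 8 / 5 | 61% | 56% |
| 10 / 10, M6 SD 1.75 | 80% | 78% |
| 5 / 10, M6 SD 1.75 | 29% | 50% |

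With no effect at either visit the false-claim rate is 4.8%. The sign of the change depends on the M6 gap and on M6 variability, and the documents give neither.

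**5. What the plan has built around M3.** A new infiltration within 3 months counts as treatment failure (section 4.2.2.3). Imputation covers inclusion and M3 (section 9.5). The per-protocol exclusions concern events before 3 months (section 9.7). The visit window is 4 days at M3 and 4 weeks at M6, and new corticosteroid infiltrations are allowed during follow-up. A confirmatory M6 analysis would need its own rules for later infiltrations and missing data.

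**6. The lighter option.** Keep M3 primary and test an M6 contrast only if M3 succeeds. A confirmed M6 result then cannot be likelier than an M3 success. With 150 analysed, gaps of 5 and 10 and correlation 0.3 to 0.7, that chance is 30% to 32%, against 85% for M6 tested alone. The feared loss remains.

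**The case for a change.** The strongest case for a change is that the protocol itself calls HA delayed, no trial summarised in section 2.2 gives a dated HA pain advantage at 3 months, and the data are already collected. If the effect follows that course, a second primary time point gains up to 44 percentage points (29% to 73%). If it fades instead, the cost is 7 or 8 (80% to 73% or 72%). No patient or visit is added.

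Part of this stands. The 35% is an extrapolation, or a difference judged worth detecting, and section 9.2 does not say which, nor for which month. The group-by-time test is not specific to M6.

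The rest does not carry. The large gains need an undiluted 10-point gap at M6, while later infiltrations and the wider window are reasons to expect dilution. Hochberg also changes what counts as success. With gaps of 5 and 10, the chance of the M3 claim itself is 28%, against 29% now, so the extra claims answer a question other than the one in section 3.1. Moving the primary endpoint also needs an amendment and new analysis rules.

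**Conclusion.** No change to the plan follows. The sample size is correct on its stated inputs, and M3 as the only primary time point is a fair choice given what the documents show. Their dated evidence concerns mainly a different contrast and does not show that a 10-percentage-point add-on gap at M3 is wrong.

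Making M6 co-primary would move the chance of a claim by between +44 and −8 percentage points across the cases above (132 analysed, SD 1.3 at M3, correlation 0.5). That is a design preference and not a correction. Dating or relabelling the 35% would clarify section 9.2 but alter no result. Analysts can take an M6 contrast with its confidence interval from the planned longitudinal model, since M6 pain is already a secondary objective. A null primary result would mean that no benefit was shown at 3 months, which is the question the trial sets itself.

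This rests on 1.3 being a reasonable residual SD for M3 VAS given baseline. Section 9.2 gives it as a baseline SD.
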